6.8 Laboratory Analyses

Any abnormal laboratory test results (hematology, clinical chemistry, or urinalysis) or other safety assessments (eg, ECGs, vital sign measurements), including those that worsen from baseline, felt to be clinically significant in the medical and scientific judgment of the investigator are to be recorded as AEs or SAEs.

However, any clinically significant safety assessments that are associated with the underlying disease, unless judged by the investigator to be more severe than expected for the subject's condition, are **not** to be reported as AEs or SAEs.

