4.2.1 Reasons for Withdrawal/Discontinuation

Subjects may withdraw from the study at any time and for any reason without prejudice to their future medical care by the investigator or at the study site. Every effort should be made to keep subjects in the study. The reasons for subjects not completing the study will be recorded. A subject may be withdrawn from the study for any of the following reasons:

1. Noncompliance with the protocol
2. A serious or intolerable adverse event(s) (AE[s]) that in the investigator's opinion requires withdrawal from the study
3. Central nervous system bleeding or life-threatening gastro-intestinal bleeding. Please also refer to the additional information in the 'Note' at the bottom of this section.
4. Laboratory safety results that reveal clinically significant hematological or biochemical changes from the baseline values
5. Symptoms of an intercurrent illness not consistent with the protocol requirements or that justify withdrawal
6. Lost to follow-up. Subjects that are considered lost to follow-up, reasonable attempts must be made to obtain information on the final status of the subject. At a minimum, 2 phone calls must be made and 1 certified letter must be sent for documentation
7. Other reasons (eg, pregnancy, development of contraindications of use of study drug, breakthrough bleeding)

8. The subject withdraws consent or the investigator or sponsor decides to discontinue the subject's participation in the study
9. Death of the subject.

Note: Bleeding events in the ITP studies are common during the first few weeks of the study before the drug has a chance to take effect; hence, all the bleeding events in this study should be recorded as an AE or SAE (based on seriousness criteria). These events should not result in removal of the subjects from the study, at least during the first 4 weeks of treatment. As the standard of care among the participating countries may differ, platelet transfusions are allowed as a rescue therapy for such events; however, these therapies may be reserved for serious or life-threatening bleeding events.

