6.4 Safety Assessments

Safety variables will include physical examination findings, vital sign measurements (systolic and diastolic blood pressure, pulse rate, respiratory rate, and temperature), ECG tracings, clinical laboratory test results (hematology, coagulation, serum chemistry, and urinalysis), bleeding score, quality of life as measured by the SF-36 score, weight, body mass index, and reporting of AEs.

Bleeding will be assessed according to the bleeding score as described by [Page et al 2007](#).

These assessments will be carried out at the time points indicated in the schedule of events.

Safety assessments will be conducted as shown in the schedule of events ([Table 2](#)).

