6.4.5.4 Reporting Adverse Events

All AEs reported or observed during the study will be recorded on the AE page in the eCRF. Information to be collected includes drug treatment, dose, event term, time of onset, investigator-specified assessment of severity and relationship to study drug, time of resolution of the event, seriousness, any required treatment or evaluations, and outcome. Adverse events resulting from concurrent illnesses, reactions to concurrent illnesses, reactions to concurrent medications, or progression of disease states must also be reported. All AEs will be followed to adequate resolution. The Medical Dictionary for Regulatory Activities (MedDRA v20.0) will be used to code all AEs. All AEs, SAEs, drug-related AEs, and drug-related SAEs will be summarized using the worst grade per NCI CTCAE v5.0 by system organ class and preferred term.

Any medical condition that is present at the time that the subject is screened but does not deteriorate should not be reported as an AE. However, if it deteriorates at any time during the study, it should be recorded as an AE.

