6.4.5.8 Assessment of Causality

The investigator's assessment of an AE's relationship to study drug is part of the documentation process, but it is not a factor in determining what is or is not reported in the study. If there is any doubt as to whether a clinical observation is an AE, the event should be reported. The relationship or association of the study drug in causing or contributing to the AE will be characterized using the following classification and criteria:

- Unrelated: This relationship suggests that there is no association between the study drug and the reported event.
- Possible: This relationship suggests that treatment with the study drug caused or contributed to the AE, ie, the event follows a reasonable temporal sequence from the time of drug administration or follows a known response pattern to the study drug but could also have been produced by other factors.
- Probable: This relationship suggests that a reasonable temporal sequence of the event with drug administration exists and, based upon the known pharmacological action of the drug, known or previously reported adverse reactions to the drug or class of drugs, or judgment based on the investigator's clinical experience, the association of the event with the study drug seems likely. The event disappears or decreases on cessation or reduction of the dose of study drug.
- Definite: This relationship suggests that a definite causal relationship exists between drug administration and the AE, and other conditions (concurrent illness, progression/expression of disease state, or reaction to concurrent medication) do not appear to explain the event. The event reappears or worsens if the study drug is re-administered.

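### Protocol 6.8, read literally, exempts ITP bleeding of expected severity from AE and SAE reporting, while 4.2.1 has all bleeding recorded, so bleeding in the TEAE and SAE tables could differ by site

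*Protocol*

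**What the plan says.** Protocol 6.8 (Laboratory Analyses) opens by asking for clinically significant abnormal results to be recorded as AEs or SAEs. Its scope is hematology, clinical chemistry and urinalysis results, "or other safety assessments (eg, ECGs, vital sign measurements), including those that worsen from baseline". An exception follows, covering "any clinically significant safety assessments that are associated with the underlying disease, unless judged by the investigator to be more severe than expected". The section states that these findings "are not to be reported as AEs or SAEs".

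Protocol 6.4 (Safety Assessments) gives the list of safety variables, which includes "clinical laboratory test results (hematology, coagulation, serum chemistry, and urinalysis), bleeding score, quality of life as measured by the SF-36 score".

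Three other places bear on the same question:

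- Protocol 4.2.1, in the note below the withdrawal reasons: "all the bleeding events in this study should be recorded as an AE or SAE (based on seriousness criteria"). No condition on severity or expectedness is attached.
- Protocol 6.4.5.4, on AE reporting: "progression of disease states must also be reported".
- Protocol 6.4.5.8, under causality: "If there is any doubt as to whether a clinical observation is an AE, the event should be reported".

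The secondary endpoint of non-skin bleeding of Grade 2 or higher appears in Protocol 7.2.4 and SAP 3.2.2.4. SAP 8.2.4 plans summary statistics for it. None of these sections says whether the events come from the bleeding score or from AE records.

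**The concern.** In ITP, bleeding is an obvious candidate for a finding associated with the underlying disease. Section 4.2.1 itself describes bleeding as common in the first weeks, which makes it easy for an investigator to call a given bleed expected. A site that follows 6.8 to the letter could leave such a bleed off the AE page. A site that follows 4.2.1 would enter it.

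Safety is part of the primary objective (Protocol 2.1, SAP 2.1), and SAP 9.1 tabulates TEAEs and SAEs by treatment group. If entry depends on which section a site follows, the bleeding rows of those tables mix drug effect with site practice. Randomization is stratified by prior TPO-receptor agonist use and baseline platelet count, not by site (Protocol 5.1), and only 12 placebo subjects are planned, so stratification does not guarantee that site practice balances across arms. The 6.8 exception also covers SAEs, which otherwise go by the 24-hour route in 6.4.5.5.

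**Working it through.** The plan states no figure on this point, so the check is a comparison of the texts.

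**1. Does 6.8 reach bleeding?** It does not name bleeding. It can reach it by two routes.

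- *Urinalysis.* Section 6.8 names urinalysis, and 6.4.4 lists occult blood among the urinalysis tests. Protocol Table 3 grades a positive dipstick as Grade 1 urinary bleeding. If that result is judged clinically significant, due to ITP and no worse than expected, 6.8 says not to report it. If it counts as a bleeding event, as Table 3 suggests, 4.2.1 says to record it. This is the most direct overlap.
- *Other safety assessments.* In 6.8, ECGs and vital signs are given only as examples. Section 6.4, whose title is Safety Assessments, lists the bleeding score and says bleeding is assessed by it. A bleed found at that assessment can be read as a clinically significant safety assessment.

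**2. Do the rules give different answers?** Take a bleed due to ITP that the investigator considers no worse than expected.

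- 4.2.1: record as an AE or SAE.
- 6.4.5.4: report, if it is regarded as disease progression.
- 6.8: do not report.

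For a bleed judged worse than expected, all three agree on reporting. The conflict is confined to bleeding of expected severity.

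**3. Does any text rank the rules?** No. Neither 4.2.1 nor 6.8 refers to the other. Section 6.4.5.8 supplies a default for a site in doubt, but a site applying the explicit instruction in 6.8 need not be in doubt.

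**4. What depends on AE entry?**

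- TEAE and SAE tables (SAP 9.1): yes.
- Bleeding score (Protocol Table 2; SAP 9.7): no. It is collected on Day 1, at Weeks 5, 9, 12 and 16, at early withdrawal or unscheduled visits, and on Day 8 for run-in subjects, whatever is entered on the AE page. It is not scheduled at Weeks 3, 7 or 11, whereas AE collection runs from consent to Week 16 (6.4.5.3), so the score does not fully replace the AE record.
- Platelet response (7.1): no.
- Non-skin bleeding of Grade 2 or higher (7.2.4): only if it is taken from AE records.

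**5. Size.** Let pA and pP be the true proportions with a bleeding AE on active drug and placebo, and f the fraction of those subjects left unrecorded, equal in both arms. The recorded difference is (1 − f)·pA − (1 − f)·pP = (1 − f)·(pA − pP). Equal under-recording shrinks the absolute difference to (1 − f) of its true value. The documents give no value for f, pA or pP, so this shows direction only. If f differs between arms, even the direction is open.

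**The case against.** The strongest reply is that 6.8 is about test results. Its heading is Laboratory Analyses, its examples are ECGs and vital signs, and its natural purpose is to keep expected ITP abnormalities, such as a low platelet count, off the AE page. Section 4.2.1 is specific to bleeding and unconditional. Section 6.4.5.1 asks for all TEAEs whatever their relationship or clinical significance, and 6.4.5.8 says to report when in doubt. On ordinary principles the specific rule prevails, and bleeding is recorded.

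That is the better reading, and it limits the point. It does not remove it. The specific rule sits in a note to the withdrawal criteria, away from the AE sections that staff would consult when deciding what to report, and 6.8 carries an explicit prohibition without exempting bleeding.

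Two further parts of the reply stand in full:

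- The laboratory overlap concerns a Grade 1 finding. Table 3 puts positive dipstick and occult stool blood at Grade 1, below the threshold of the secondary endpoint, and 6.4.4 lists no stool test. Macroscopic urinary or gross gastrointestinal bleeding is an overt event that 4.2.1 plainly covers.
- Investigators are blinded (5.6), and the bleeding endpoint receives summary statistics only, so no planned hypothesis test of it is at risk.

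**Conclusion.** The contradiction is in the current text and is worth correcting, within limits. Sections 6.8 and 4.2.1 give opposite instructions for ITP bleeding of expected severity, 6.4.5.4 is in tension with 6.8, and no text settles the order. AE and SAE recording of such bleeding, and so the TEAE and SAE tables, could differ by site. This assumes that some sites read 6.8 literally; the documents do not show how many would.

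A reader might infer more, and the documents do not support it:

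- *That the recording of bleeding as a whole depends on the site.* The bleeding score is collected on its own schedule, and 6.8 keeps bleeds judged worse than expected reportable.
- *That the secondary bleeding endpoint is compromised.* Its source is not stated. Grading by site with separate skin rows fits Table 3; the words allowing for higher grades fit it less well, because Table 3 stops at Grade 2. The wording does not decide the matter.
- *That the primary efficacy result is at risk.* Platelet response does not use AE data.
- *That the loss can be put as a percentage.* No document figure allows that.

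**What to change.** Add one sentence to Protocol 6.8: the underlying-disease exception does not apply to bleeding events, which are recorded as an AE or SAE under 4.2.1. Include the cross-reference to 4.2.1, and ideally repeat it in 6.4.5.4, where staff look for reporting rules. Leave the exception in place for non-bleeding disease findings such as low platelet counts; narrowing it further goes beyond what the conflict requires. The change concerns recording only and alters no clinical management.

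The cost is one protocol sentence, a site memo and slightly more AE pages.

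This does not settle the source of the endpoint for non-skin bleeding of Grade 2 or higher. That is a separate gap, which a line in SAP 8.2.4 naming the source would close.

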6.9 Sample Collections

The total volume of blood collected for each assessment is discussed in each specific laboratory manual.

6.10 Pharmacogenomic Screening

A 6-mL whole blood sample for genotyping will be drawn at Baseline (Day 1, before dosing) from subjects who have consented to participate in the genetic analysis component of the study to potentially explore genetic polymorphisms of the enzymes (eg, UGT1A1) responsible for the metabolism of SKI-O-703 and the association of these genetic polymorphisms with the PK of SKI-O-703. Further details of blood collection and processing will be provided in the laboratory manual.

7 Statistical and Analytical Plan

7.1 Primary Endpoint - Platelet Response

- Patient platelet response is defined as platelet count $\geq 30,000/\mu\text{L}$ and doubling the baseline (average of 2 previous counts), at any visit during the treatment period and without the use of rescue medication

7.2 Secondary Endpoints

7.2.1 Subjects Achieving Two or More Pre-specified Platelet Counts

- Subjects able to achieve 2 or more consecutive platelet counts of $\geq 30,000/\mu\text{L}$ separated by at least 5 days and without use of rescue medication
- Subjects able to achieve 2 or more consecutive platelet counts of $\geq 30,000/\mu\text{L}$ with an increase of platelet count of $\geq 20,000/\mu\text{L}$ from baseline separated by at least 5 days and without use of rescue medication
- Subjects able to achieve 2 or more consecutive platelet counts of $\geq 50,000/\mu\text{L}$ separated by at least 5 days and without use of rescue medication
- Subjects able to achieve 2 or more consecutive platelet counts of $\geq 100,000/\mu\text{L}$ during the treatment period, separated by at least 5 days and without use of rescue medication
- Subjects able to achieve platelet counts of $\geq 50,000/\mu\text{L}$ at 3 of the last 4 visits.

7.2.2 Change from Baseline in Platelet Counts

- Change from baseline in the average of the last 2 platelet counts during the treatment period

For each subject, the change from baseline in the mean of the last 2 platelet counts during the treatment period will be calculated. For those subjects with only 1 platelet count during treatment period, the change from baseline in the single platelet count will be used.

7.2.3 Time to First Platelet Response

- Time to first platelet response ($>30,000/\mu\text{L}$ and $2 \times$ baseline)

For each subject, the time of the first platelet response is the first visit during treatment period in which platelet count $\geq 30,000/\mu\text{L}$ without use of rescue medication.

7.2.4 Others

- Number of subjects receiving rescue medication at least once during treatment period
- Subjects with at least one Grade 2 or higher non-skin bleeding event during treatment period.

For each endpoint, a subject will be considered to have had an event if the event was observed at least once during the treatment period for rescue medication, and during treatment or follow-up period for bleeding event.

7.3 Exploratory Endpoints

7.3.1 Peak Platelet Count

- Peak platelet counts during the treatment period without use of rescue medication

For each subject, peak platelet count is subject's highest platelet count during the treatment period, without use of rescue medication.

7.3.2 Bleeding Score

The ITP bleeding assessment score as described by [Page et al. 2007](#) will be used to characterize bleeding tendency.

Table 3 The ITP Bleeding Score Assessment

Site	Bleeding Grade		
	0	1	2
Skin [physical Examination (PE)]	None	1–5 bruises and/or scattered petechiae	>5 bruises with size >2 cm and/or diffuse petechiae
Oral (PE)	None	1 blood blister or >5 petechiae or gum bleeding that clears easily with rinsing	Multiple blood blisters and/or gum bleeding
Skin (Hx)	None	1–5 bruises and/or scattered petechiae	>5 bruises with size >2 cm and/or diffuse petechiae
Oral (Hx)	None	1 blood blister or >5 petechiae and/or gum bleeding <5 min	Multiple blood blisters and/or gum bleeding >5 min
Epistaxis	None	Blood when blowing nose and/or epistaxis <5 min (per episode)	Bleeding >5 min (per episode)
Gastrointestinal	None	Occult blood	Gross blood
Urinary	None	Microscopic (+ve dipstick)	Macroscopic

Site	Bleeding Grade		
	0	1	2
Gynecological	None (normal period)	Spotting not at time of normal period	Bleeding >spotting not at time of period or very heavy period
Pulmonary	None	N/A	Yes
Intracranial haemorrhage	None	N/A	Yes
Subconjunctival haemorrhage	None	Yes	N/A

Abbreviations: ITP, immune thrombocytopenia; PE, physical examination; N/A, not applicable

Note: In case of a breakthrough bleeding, the subjects will discontinue the trial.

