4.2.2 Handling of Withdrawals

Subjects are free to withdraw from the study or study drug at any time upon request. Subject participation in the study may be stopped at any time at the discretion of the investigator or at the request of the sponsor.

Subjects who discontinue study drug or active participation in the study will no longer receive study drug. When a subject withdraws from the study drug or active participation in the study, the reason(s) for withdrawal shall be recorded by the investigator on the relevant page of the electronic case report form (eCRF). Whenever possible, all subjects who discontinue study drug permanently or withdraw from the study prematurely will undergo all end-of-study assessments. Subjects who fail to return for final assessments will be contacted by the site in an attempt to have them comply with the protocol. Following a minimum of 2 documented unsuccessful telephone calls, a registered letter will be sent to the subject in a final attempt to ensure protocol compliance.

It is vital to obtain follow-up data on any subject withdrawn because of an AE or SAE. In every case, efforts must be made to undertake protocol-specified safety follow-up procedures.

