6.1 Study Visits

The total study duration will be 20 weeks per subject, which consists of up to 4 weeks of screening period. The treatment period will be 12 weeks (split into 1-week safety run-in period and 11-week treatment period for the first 5 subjects). The post-treatment follow-up period will be of 4 weeks. Each assessment will be carried out at timepoints indicated in the Schedule of Events table and clarified in the footnotes presented below the table. The schedule of events is summarized in [Table 2](#).

Table 2 Schedule of Events

	Screening (D-28 to D-1)	On-treatment Visits					Follow-up Clinic Visits	Early Withdrawal/ Unscheduled visit
		W1 (D1), W5 and 9 (± 3 days)	W1D4 (± 1 day)	W2D8 (± 2 days)	W3, 7, 11 (± 3 days)	W12 (D84 or D85) (EOT) (± 3 days)	End of Study W16 (± 1 week)	
Clinic visits	X	X ^a		X ^{a*}	X ^a	X ^a	X ^a	X
Informed consent	X							
Inclusion/Exclusion criteria	X	X ^h						
AEs		<----->						X
Concomitant medications	X	X		X*	X	X	X	X
Height	X							
Weight	X	X		X*		X	X	X
Physical examination/medical history ^b	X	X		X*	X	X	X	X
ECG ^c	X	X		X		X	X	X
Vital signs	X	X		X*	X	X	X	X
Urinalysis	X	X		X*	X	X	X	X
Hep B & C, HIV, HBV DNA, HCV RNA	X							
Pregnancy test/ FSH ^d	X	X				X	X	X
Contraception status	X	X		X*		X	X	X
ABO and Rh blood type	X							
Serum chemistry	X	X		X*	X	X	X	X
Hematology, differential	X	X	X ^{a,e}	X ^{a,e}	X	X	X	X
PT/INR PTT	X					X		
Study drug dispensing		X			X			X ^f
Study drug administration		X	X	X*	X	X		X ^f
Blood samples for PK and PD assessments ^g		X ^h		X*		X		

	Screening (D-28 to D-1)	On-treatment Visits					Follow-up Clinic Visits End of Study W16 (± 1 week)	Early Withdrawal/ Unscheduled visit
		W1 (D1), W5 and 9 (± 3 days)	W1D4 (± 1 day)	W2D8 (± 2 days)	W3, 7, 11 (± 3 days)	W12 (D84 or D85) (EOT) (± 3 days)		
Bleeding Score ⁱ		X		X*		X	X	X
Quality of life using SF-36 score		X				X	X	X
Pharmacogenomic screening		X ^j						

Abbreviations: AEs, adverse events; D, Day; ECG, 12-lead electrocardiogram; EOT, end-of-treatment; FSH, follicle stimulating hormone; HBV, hepatitis B virus; HCV, hepatitis C virus; hep, hepatitis; HIV, human immunodeficiency virus; PD, pharmacodynamics; PK, pharmacokinetics; PT/INR, prothrombin time/international normalized ratio; PTT, partial thromboplastin time; W, Week

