- * Subjects in the safety run-in period will have clinic visit on Week 2/Day 8 (± 2 days) for the mentioned assessments including hematology (differential) tests. For other subjects, this visit will be laboratory only visit to perform hematology (differential) tests only.
- a Clinic / laboratory visit windows are about ± 3 days for all dosing period and laboratory visits and about ± 1 week for clinic follow-up visits. The W12/D84 or D85 (EOT) visit should be performed while on therapy.
- b Complete physical examination at Screening and abbreviated physical examination at other visits.
- c For all subjects: predose ECG on the first day of dosing and on Day 1 of each subsequent week as specified in the table above. For subjects in the safety run-in subsets and PK/PD subset who are in safety run-in subset only: ECG on the first day of dosing at predose, 1, 2, 4, 8, and 12 hours (± 10 min) after the study drug administration.
- d For women of childbearing potential only: Serum pregnancy tests are performed at Screening. To confirm pregnancy, urine pregnancy test will be performed locally on Day 1 prior to randomization and prior to study drug administration on clinic visit days at mentioned timepoints. If urine pregnancy test is negative, dosing will be started; if urine pregnancy test is positive then with-hold dosing and perform a serum pregnancy test. FSH testing is needed at Screening for post-menopausal female subjects only.
- e Laboratory only visits will be performed on Day 4 ± 1 day (Week 1) for all subjects and on Week 2/Day 8 (± 2 days) for subjects other than those enrolled in the safety run-in period.
- f Study drug dispensing and administration can occur at unscheduled visit.
- g Samples to be collected as follows:

For the subjects in the safety run-in period only (for PK only; no PD assessments):

- Day 1: morning predose, 0.25 (± 5 min), 0.5 (± 5 min), 1, 2, 4, 8, and 12 hours (± 10 min) (evening predose).
- Day 8 (± 2 days): morning predose, 0.25 (± 5 min), 0.5 (± 5 min), 1, 2, 4, 8, and 12 hours (± 10 min) (evening predose).
- Week 12: morning predose, 0.25 (± 5 min), 0.5 (± 5 min), 1, 2, 4, 8, and 12 hours (± 10 min).

For the subjects in the PK/PD subset only (for PK/PD):

- Day 1: morning predose, 0.25 (± 5 min), 0.5 (± 5 min), 1, 2, 4, 8, and 12 hours (± 10 min) (evening predose).
- Week 12: morning predose, 0.25 (± 5 min), 0.5 (± 5 min), 1, 2, 4, 8, and 12 hours (± 10 min).

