#### *3.2.3.2. Bleeding Score*

The ITP bleeding assessment score as described by Page et al. 2007 will be used to characterize bleeding tendency.

Table 3-1 The ITP Bleeding Score Assessment

Site	Bleeding Grade		
	0	1	2
Skin [physical Examination (PE)]	None	1–5 bruises and/or scattered petechiae	>5 bruises with size $>2$ cm and/or diffuse petechiae
Oral (PE)	None	1 blood blister or $>5$ petechiae or gum bleeding that clears easily with rinsing	Multiple blood blisters and/or gum bleeding

Site	Bleeding Grade		
	0	1	2
Skin (Hx)	None	1–5 bruises and/or scattered petechiae	>5 bruises with size >2 cm and/or diffuse petechiae
Oral (Hx)	None	1 blood blister or >5 petechiae and/or gum bleeding <5 min	Multiple blood blisters and/or gum bleeding >5 min
Epistaxis	None	Blood when blowing nose and/or epistaxis <5 min (per episode)	Bleeding >5 min (per episode)
Gastrointestinal	None	Occult blood	Gross blood
Urinary	None	Microscopic (+ve dipstick)	Macroscopic
Gynecological	None (normal period)	Spotting not at time of normal period	Bleeding >spotting not at time of period or very heavy period
Pulmonary	None	N/A	Yes
Intracranial haemorrhage	None	N/A	Yes
Subconjunctival haemorrhage	None	Yes	N/A

- abbreviation: ITP, immune thrombocytopenia; PE, physical examination; N/A, not applicable
- Note: In case of a breakthrough bleeding, the patients will discontinue the trial.

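### A table note orders subjects off the trial after an undefined breakthrough bleeding, against the protocol's own retention and rescue rules for bleeders

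*Protocol*

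**What the plan says.** The note under Table 3 in protocol 7.3.2 reads "In case of a breakthrough bleeding, the subjects will discontinue the trial". The same note under Table 3-1 in SAP 3.2.3.2 reads "In case of a breakthrough bleeding, the patients will discontinue the trial". Neither document defines the term or ties it to a grade in the table.

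Three other places give instructions for subjects who bleed:

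- Protocol 4.2.1 introduces its list with "A subject may be withdrawn from the study for any of the following reasons". Item 7 of that list is "Other reasons (eg, pregnancy, development of contraindications of use of study drug, breakthrough bleeding". Item 3, listed separately, is central nervous system or life-threatening gastrointestinal bleeding.
- The Note that closes 4.2.1 explains that early bleeding is to be expected in ITP studies before the drug can work, and says "These events should not result in removal of the subjects from the study, at least during the first 4 weeks of treatment".
- Protocol 5.8.1, echoed in SAP 7.2, lists the rescue treatments allowed for bleeding. It says subjects should be withdrawn for two kinds of bleed, central nervous system and life-threatening gastrointestinal, and names no others.

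After a premature withdrawal, 4.2.2 asks that, where possible, "all subjects who discontinue study drug permanently or withdraw from the study prematurely will undergo all end-of-study assessments". Protocol 1.4 promises follow-up for the full intended duration to subjects who stop treatment or cannot adhere to the protocol. It does not mention subjects who have left the trial.

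**The concern.** The note is a firm instruction to leave the trial, with no time limit, for an event that each site must define for itself. Elsewhere the protocol treats bleeding as something to rescue and follow. Nothing says which text prevails, and sites in Korea, the US and the EU could resolve the conflict differently.

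The statistical stake is outcome-related missingness. Bleeding is linked to low platelet counts, so subjects removed for bleeding are not a random sample. If the drug works, removal may also be more frequent on placebo, where one subject of the planned 12 is 8.3% of the group (1/12). Several SAP analyses are built to use counts taken after a bleed and its rescue. Those counts exist only if the subject stays.

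**Working it through.** **The texts side by side.** Take a subject who bleeds on Day 20, receives permitted rescue, and has neither of the two bleeds named in 5.8.1. Under the 4.2.1 Note the subject stays. Under 5.8.1 the subject is rescued, with no call to withdraw. Under the table note, if the site calls the bleed a breakthrough, the subject leaves the trial. The table note is the outlier.

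**Counts at stake.** The plan gives no figure for this point, so there is none to reproduce. The inputs are the hematology rows and visit columns of protocol Table 2, from the Day 4 laboratory visit (footnote e: "Laboratory only visits will be performed on Day 4") to the column headed "W12 (D84 or D85) (EOT". Each weekly visit is taken as the first day of its week (so Week 2 is Day 8), and Week 12 as Day 84. The 8 post-baseline on-treatment counts then fall on Days 4, 8, 15, 29, 43, 57, 71 and 84.

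For removal on day r:

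- kept = number of those days ≤ r
- lost = 8 − kept

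| Removal on day | Kept | Lost |
|---|---|---|
| 8 or 14 | 2 | 6 |
| 21 or 28 | 3 | 5 |
| 29 | 4 | 4 |
| 43 | 5 | 3 |
| 57 | 6 | 2 |
| 71 | 7 | 1 |

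Visit windows move these figures at the margin. Week 5 is Day 29 ± 3, so a visit on Day 26 to 28 leaves 4 counts for a subject removed on Day 28. In the other direction, the Day 8 visit has a window of ± 2 days, so a subject removed on Day 8 before a visit due on Day 9 or 10 keeps 1. Hematology is also marked in the early-withdrawal column, so one further count may be obtained.

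**Counts beyond the 28-day rescue window if the subject is kept.** These are the visits later than (rescue day + 28).

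- Rescue on Day 8 or 14: the window ends on Day 36 or 42, leaving 4 counts (Weeks 7, 9, 11, 12).
- Rescue on Day 21 or 28: the window ends on Day 49 or 56, leaving 3 counts (Weeks 9, 11, 12). For rescue on Day 28, a Week 9 visit on Day 54 to 56 falls inside the window and leaves 2.
- If the subject has left the trial, no scheduled on-treatment count remains.

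**Where the loss falls.**

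1. *28-day-window sensitivity analysis (SAP 8.1.2).* It credits responses seen more than 28 days after rescue. A removed subject cannot show one.
2. *Treatment-policy sensitivity analysis (SAP 8.1.2).* It aims to use all visits to Week 12 whatever happens. The missing counts would be imputed under missing at random from treatment, baseline, earlier counts and prior TPO-receptor agonist use. Bleeding and rescue are not in that list.
3. *Change from baseline in the last 2 counts (SAP 8.2.2).* The main analysis uses observed data, so early counts stand in for late ones.
4. *Counts of at least 50,000/µL at three of the last four visits.* Removal by Day 28 loses all four of the last scheduled visits (Weeks 7, 9, 11, 12). SAP 8.2.1 excludes visits with missing results and sets undetermined cases to non-response. The subject is therefore judged on earlier visits or counted as a failure.

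**Primary analysis (SAP 8.1.1).** Counts after rescue are already set to missing, a response before removal still counts, and undetermined response becomes non-response. Removal changes the result only for a bleeder who would not have needed rescue and would first have responded later.

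**The case against.** **Will against may.** A reader might infer that the main fault is a mandatory note set against a discretionary list. The documents do not support giving that first place. The list in 4.2.1 is a catalogue of grounds that also contains death and loss to follow-up, and firmer rules for listed items appear elsewhere. The bleeds in item 3 should lead to withdrawal under 5.8.1, and significant deviations lead to withdrawal under 11.2.2. The difference in wording is a secondary inconsistency. The conflicts with the 4.2.1 Note and with 5.8.1 carry the point.

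**Breakthrough may mean late bleeding.** The Note speaks of bleeding before the drug can take effect, so breakthrough could be read as bleeding after that. That reading would remove the clash with the 4-week rule, but nothing in the documents states it. The tension with 5.8.1 would remain, because 5.8.1 has no time limit.

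**The Day 8 to Day 28 case is the worst one.** This is fair: it is the period in which 4.2.1 tells sites to keep bleeders, and removal from Day 29 on keeps at least 4 counts on nominal days. It is also the period in which the two instructions collide.

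**Safeguards exist.** SAP 8.2.2 includes a control-based missing-not-at-random analysis, which partly covers change from baseline. Protocol 1.4 shows an intention to follow subjects, but it covers stopping treatment and not leaving the trial. Any other withdrawal loses the same counts, so the note changes how often this happens, and the documents do not say how often.

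**Conclusion.** The note is wrong as written. It is a firm rule to leave the trial, for an undefined event and without a time limit, and it conflicts with the retention rule in the 4.2.1 Note and the rescue pathway in 5.8.1. The wording conflict is certain except under an unstated reading of breakthrough, and even that reading leaves the tension with 5.8.1.

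The consequence is conditional on sites following the note. On nominal days, a subject removed between Day 8 and Day 28 then loses 5 or 6 of 8 on-treatment counts, with small shifts within visit windows; later removal loses fewer. The loss affects two sensitivity analyses and two secondary endpoints.

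A reader might infer that the primary result is compromised. The documents do not support that: the primary rules already discard counts after rescue and treat undetermined cases as non-response. Neither the number of subjects affected nor the size or direction of any bias can be derived, because no rate of bleeding or of withdrawal for bleeding is given. The point is minor.

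**What to change.** Delete the note under Table 3 in protocol 7.3.2 and under Table 3-1 in SAP 3.2.3.2. Alternatively, replace it in both with a cross-reference to protocol 4.2.1 and 5.8.1. Withdrawal for bleeding then follows those sections, and other bleeders stay in follow-up with their scheduled counts. Defining breakthrough bleeding would help readers of item 7 in 4.2.1, but it would not by itself remove the mandatory exit.

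The cost is one sentence in each document. The protocol change can go into the next amendment, which needs IRB/IEC approval under 11.2.1 in any case. It requires no new visits, assessments or subjects.
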